6.4. Interim Analyses and Data Monitoring⁴

Based on FDA recommendation the trial will be subject to a Temporary Halt to evaluate the study data in an interim analysis and create an interim report.

The interim report will be shared with FDA as post-approval supplement. Based on this report and subsequently feedback from FDA, it will be decided if the MC2-01-C6 study should be permanently closed or re-activated.

Interim analysis will be conducted on complete data from all subjects who had been enrolled into the trial at the time of interim analysis. Interim analysis will include the analysis of all endpoints initially planned in the clinical study protocol.

6.5. Multi-center Studies

Data from all centers will be merged and analyzed as one population for all study endpoints.

6.6. Multiple Testing

No adjustment for multiplicity is planned.

⁴ This section is based on the section 8.11 “Interim analysis” of clinical study Protocol including Amendment.

**MC2-01-C6_STATISTICAL ANALYSIS PLAN_Final 3.0_07 September 2020**

7. Summary of Study Data

Demographic and other baseline characteristics and safety data will be summarized by time point of assessment and listed.

Default Summary Statistics

The default summary statistics for quantitative and ordinal variables will be the number of observations (n), mean, standard deviation (SD), median, minimum (Min) and maximum (Max).

Default Frequency Tabulations

For qualitative variables, the number and percentage (n, %) of subjects with non-missing data per category and total number of subjects with non-missing data where applicable will be the default summary presentation.

For AEs, medical history, concomitant medications and protocol deviations, however, the denominator for the percentage calculation will be the number of subjects in the corresponding population.

The number of decimals for each descriptive statistic will be determined by the following rules:

- mean, median: +1 decimal symbols compared to the analyzed variable values;
- standard deviation: +1 decimal symbols compared to the analyzed variable values;
- first (Q1) and third (Q3) quartiles: +1 decimal symbols compared to the analyzed variable values;
- minimum and maximum values: the same as for the analyzed variable values;
- percentages will be rounded to one decimal symbol;
- confidence intervals will be presented with accuracy of the estimated value.

The maximum number of decimal places in the statistical report is four. If some descriptive statistic has more than four decimal places after above mentioned rules application, this value will be rounded to four decimal places.

Statistical Tests and Common Calculations

Unless otherwise specified in the description of the analyses, the following arrangements will be applied:

- 95% two-sided confidence intervals (CI);
- CIs for mean values will be calculated based on normal distribution (SAS procedure UNIVARIATE with CIBASIC option);
- CIs for proportions will be computed using the exact (Clopper-Pearson) method.

For descriptive statistics, the following rules will be applied:

- “<X.XX” results (e.g. below the limit of quantification, BLQ) for safety laboratory parameter values will be imputed with numeric result calculated as X.XX – 0.01. The number to be subtracted will be defined based on number of decimal places in observed values (e.g., if number of decimal places is 0 subtract 1, if number of decimal places is 1 subtract 0.1, etc.). Imputed data will be used in summaries and calculations, but original

**MC2-01-C6_STATISTICAL ANALYSIS PLAN_Final 3.0_07 September 2020**

result will be listed.

For quantitative measurements, changes from baseline will be calculated as [value at post-baseline visit X – baseline value].

The baseline value for a variable in common cases is defined as the last non-missing value collected before the first study drug application.

Study day for each event will be calculated from the reference start date (date when subject was first exposed to study drug).

If the date of the event is on or after the reference date, then

$$\text{study day} = (\text{date of event} - \text{reference date}) + 1.$$

If the date of the event is prior to the reference date, then

$$\text{study day} = (\text{date of event} - \text{reference date}).$$

For partial dates study day will not be calculated.

The following visit windows were defined in the clinical study protocol:

| Visit Name | Visit Short Name | Anchor | Target Day | First day of the visit window | Last day of the visit window |
|-------------------|------------------|-------------------|------------|-------------------------------|------------------------------|
| Screening Visit 1 | SV1 | First application | - | -42 | -8 |
| Screening Visit 2 | SV2 | First application | - | -7 | -4 |
| Visit 1 (Day 0) | V1 (Day 0) | First application | 1 | 1 | 1 |
| Visit 2 / Week 2 | V2/Week 2 | First application | 15 | 13 | 17 |
| Visit 3 / Week 4 | V3/Week 4 | First application | 29 | 27 | 31 |
| Visit 4 / Week 6 | V4/Week 6 | First application | 43 | 41 | 45 |
| Visit 5 / Week 8 | V5/Week 8 | First application | 57 | 55 | 59 |
| Follow-up Visit | FU | Last application | 15 | 13 | 17 |

Assessments performed out of the planned visit windows will be assigned to the nearest of the surrounding planned visits if there is no valid result from a planned assessment for this visit. If assessments at both surrounding visits are missing and they are equidistant, the assignment is performed to the later one. Otherwise the assessments will not be included in summaries and will be listed only.

Unscheduled and early termination visit assessment can be assigned to the planned visit in a similar manner. Unscheduled assessment can also be used in the derivations such as baseline or most extreme post-baseline assessments. All assessments including unscheduled should be presented by subject in the data listings.

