8.2 Sample Size and Power Considerations

The choice of sample size in this trial is not based on statistical considerations, but rather on regulatory considerations with respect to common practice in maximum use studies evaluating pharmacokinetic profiles and evidence of HPA safety.

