7.2. Protocol Deviations

Number and percentage of subjects with at least one protocol deviation and at least one major protocol deviation will be tabulated by category and subcategory and overall (Allocated to treatment set). All protocol deviations will be listed (All Enrolled subjects).

Major protocol violations include but are not limited to:

- Informed consent not received or provided after the first study visit;
- Inclusion/exclusion criteria violations in subjects allocated to treatment;
- Use of prohibited concomitant medication or non-drug therapy that may affect study results or their interpretation;
- Week 4 assessments performed more than 14 days after the scheduled date;
- Week 8 assessments performed more than 14 days after the scheduled date;

Major protocol violations will be finalized and approved by MC2 at the data review meeting.

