**MC2-01-C6_STATISTICAL ANALYSIS PLAN_Final 3.0_07 September 2020**
APPENDIX 1 TFLs ShellsMC2 Therapeutics
MC2-01-C6**Table 14.3.4.1.2 Incidence of HPA Axis Suppression**
HPA population
Page X of X

| | | Total (N = XX) |
|-----------------------------------|-----------------------------------|--------------------------------------|
| HPA axis suppression | | |
| Overall | n' (%) [1] n (%) [2] 95% CI | XX (XX.X) XX (XX.X) XX.X, XX.X |
| Visit 3 / Week 4 | n' (%) [1] n (%) [2] 95% CI | XX (XX.X) XX (XX.X) XX.X, XX.X |
| Visit 5 / Week 8 | n' (%) [1] n (%) [2] 95% CI | XX (XX.X) XX (XX.X) XX.X, XX.X |
| HPA axis suppressed at Week 4 | n' (%) [3] n (%) [2] 95% CI | XX (XX.X) XX (XX.X) XX.X, XX.X |
| HPA axis not suppressed at Week 4 | n' (%) [3] n (%) [2] 95% CI | XX (XX.X) XX (XX.X) XX.X, XX.X |

CI=Confidence Interval; HPA=Hypothalamic-pituitary-adrenal.

N: the number of subjects in the HPA population. n: the number of subjects within a specific category. n': the number of valid observations.

[1] Subjects having any post-baseline values (for 'Overall' category) or values at the corresponding visit. Percentage is calculated as $(100 \times n/N)$.

[2] Percentages are based on the corresponding number of valid observations.

[3] Subjects with corresponding HPA suppression status at Week 4 having values at Visit 5 / Week 8. Percentage is calculated based on number of subjects with corresponding HPA suppression status at Week 4.

Confidence interval is calculated using Clopper-Pearson method.

Adrenal suppression is defined as the 30-minute post-stimulation serum cortisol level below 18 ug/dL (500 nmol/L).

Data MATRIX

SF_STAT001_ver 2_Eng
Approval Date 19 July 2017

MC2-01-C6_STATISTICAL ANALYSIS PLAN_Final 3.0_07 September 2020

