APPENDIX 1 TFLs Shells

 MC2 Therapeutics
 MC2-01-C6

Listing 16.2.8.7 ACTH Challenge Test
 All Enrolled subjects
 Page X of X

| Country/Site ID/ Subject ID | Age(Years)/ Sex/Race/ Ethnicity | Visit | Date, Time of assessment/ Study Day | Parameter (Units) | HPA Axis Suppression Noted | Result | Reason if Not Done |
|--------------------------------|---------------------------------------|--------|---|---|----------------------------------|--------|-----------------------|
| XXX/XX/XXXXXX | 14/F/A/NHL | Scr V2 | YYYY-MM-DD HH:MM/ XX | Serum cortisol pre-stimulation (nmol/L) | | XX.X | |
| | | | YYYY-MM-DD HH:MM/ XX | Serum cortisol post-stimulation (nmol/L) | No | XX.X | |
| | V3/Week 4 | | YYYY-MM-DD HH:MM/ XX | Serum cortisol pre-stimulation (nmol/L) | | XX.X | |
| | | | YYYY-MM-DD HH:MM/ XX | Serum cortisol post-stimulation (nmol/L) | No | XX.X | |
| | | | YYYY-MM-DD HH:MM/ XX | Serum cortisol pre-stimulation (nmol/L) | | XX.X | |
| | | | YYYY-MM-DD HH:MM/ XX | Serum cortisol post-stimulation (nmol/L) | No | XX.X | |
| | V5/Week 8 | | YYYY-MM-DD HH:MM/ XX | Serum cortisol pre-stimulation (nmol/L) | | XX.X | |
| | | | YYYY-MM-DD HH:MM/ XX | Serum cortisol post-stimulation (nmol/L) | No | XX.X | |
| | | | YYYY-MM-DD HH:MM/ XX | Serum cortisol pre-stimulation (nmol/L) | | XX.X | |
| | | | YYYY-MM-DD HH:MM/ XX | Serum cortisol post-stimulation (nmol/L) | No | XX.X | |
| | FU | | YYYY-MM-DD HH:MM/ XX | Serum cortisol pre-stimulation (nmol/L) | | XX.X | |
| | | | YYYY-MM-DD HH:MM/ XX | Serum cortisol post-stimulation (nmol/L) | No | XX.X | |
| ... | | | | | | | |

Country: CZE=Czech Republic, HUN=Hungary, DEU=Germany; Sex: F=Female, M=Male;

Race: A=Asian, B=Black or African American, W=White, O=Other; Ethnicity: HL=Hispanic or Latino, NHL=Not Hispanic or Latino.

^ indicates reported visit is different from the analysis visit after windowing was performed.

Path to the program code, date and time of output/ Datasets used

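### The SAP section 7 windowing rule can move a Week 4 or Week 8 ACTH, calcium or urine test that is a week or more off target to a visit with no row in the primary tables

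*SAP*

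**What the plan says.** SAP section 7 has a single window table for all variables. The entries that matter (target, first and last study day) are "Visit 3 / Week 4 | V3/Week 4 | First application | 29 | 27 | 31" and "Visit 4 / Week 6 | V4/Week 6 | First application | 43 | 41 | 45". Week 2 has target 15 (13–17) and Week 8 has target 57 (55–59).

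For results outside the windows: "Assessments performed out of the planned visit windows will be assigned to the nearest of the surrounding planned visits if there is no valid result", with the condition that the competing result comes from an assessment planned for that visit. For ties: "If assessments at both surrounding visits are missing and they are equidistant, the assignment is performed to the later one". Anything that cannot be placed is listed only.

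The schedule (Protocol Table 7-1, SAP Table 1) is narrower than the window table:
- The ACTH test is done at SV2, Week 4 and Week 8, and conditionally at follow-up.
- Serum chemistry and morning urine are done at SV2, Week 4 and Week 8. At Week 6 they are done only as a repeat after a high Week 4 value, and at follow-up only as a repeat after a high Week 8 value.
- None of these tests is scheduled at Week 2.

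The on-treatment rows in the primary shells are Week 4 and Week 8 only (Tables 14.3.4.1.1, 14.3.4.1.2 and 14.3.4.2.1). Table 14.3.4.1.2 also has an Overall row based on any post-baseline value, and it splits the Week 8 result by Week 4 suppression status. Under SAP 9.5 the HPA percentage is based on the number of valid tests at each visit.

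**The concern.** The rule looks for the nearest planned visit but does not say that the visit must be one at which the test in question is routinely done. For ACTH, Week 2 and Week 6 never hold a planned result that would block the assignment, so a displaced test can always land there. For calcium and urine, Week 6 is usually empty as well. When it is not, it holds the repeat, and a late Week 4 result nearer to Week 6 becomes listing-only.

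In either case the result has no row in the by-visit primary tables. The subject leaves the Week 4 or Week 8 denominator. If the Week 4 ACTH test is the one displaced, the subject also leaves the Week 8 split by Week 4 status. Calcium has less protection than HPA because Table 14.3.4.2.1 has no Overall row.

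**Working it through.** **Reproducing the plan's windows.** SAP section 7 defines study day = (date − first application) + 1. Protocol Table 7-1 places the visits at Day 14, 28, 42 and 56, each ± 2, counting first application as Day 0. Adding 1 gives targets 15, 29, 43 and 57 with windows 13–17, 27–31, 41–45 and 55–59. These match the SAP table.

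**Applying the literal rule.** Outside a window, compare the distances to the two neighbouring targets, with ties to the later visit when both are missing.

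| Test | Study day | Distances to targets | Assigned to |
|---|---|---|---|
| Week 4, 3–6 days late | 32–35 | 3–6 from 29; 11–8 from 43 | Week 4 |
| Week 4, 7 days late | 36 | 7 from 29; 7 from 43 (tie) | Week 6 |
| Week 4, 8–11 days late | 37–40 | 8–11 from 29; 6–3 from 43 | Week 6 |
| Week 4, 12–14 days late | 41–43 | inside the Week 6 window | Week 6 |
| Week 4, 7 days early | 22 | 7 from 15; 7 from 29 (tie) | Week 4 |
| Week 4, 8–11 days early | 21–18 | 6–3 from 15; 8–11 from 29 | Week 2 |
| Week 8, 8–11 days early | 49–46 | 6–3 from 43; 8–11 from 57 | Week 6 |

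The out-of-window sentence therefore moves a late Week 4 test on five days (36–40). On days 41–43 it is the Week 6 window itself that captures the test.

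**If a valid Week 6 repeat exists (calcium or urine).** On days 37–40 the nearest visit is already occupied, so the Week 4 result is listed only. On day 36 the tie rule requires both visits to be missing, so the case is undefined.

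**The narrower reading for ACTH.** If only Week 4 (29) and Week 8 (57) are eligible, days 32–42 stay at Week 4. Day 43 is 14 days from each target and goes to Week 8 if both are missing.

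**Size, if one subject were affected.** SAP 6.1 places the interim analysis after 7 treated subjects complete. Assume that all 7 are in the HPA population and have a valid Week 4 test. With zero events the Clopper-Pearson upper 95% limit is 1 − 0.025^(1/n):
- n = 7: 1 − 0.025^(1/7) = 41.0%
- n = 6: 1 − 0.025^(1/6) = 45.9%

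The lost share of the denominator is 1/7 = 14.3%. At the planned enrolment of about 30, the same loss moves the limit from 11.6% (0/30) to 11.9% (0/29). In the extreme case where the displaced subject is the only suppressed one, the Week 4 row changes from 1/7 (14.3%, 95% CI 0.4% to 57.9%) to 0/6 (0%, 95% CI 0% to 45.9%).

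**The case against.** The strongest reply is that the rule speaks of a planned assessment for the visit and of assessments being missing, and a test is normally planned or missing only where it is scheduled. SAP 9.5 also presents the calcium endpoints by visit as scheduled in Table 1, and the shells carry only Week 4 and Week 8 as on-treatment rows. This reading is tenable. It would keep a Week 4 ACTH test up to 13 days late at Week 4. It does not clearly settle calcium and urine, because Table 1 does plan those tests at Week 6, conditionally. The SAP does not say which reading applies, and the two can produce different primary tables.

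The loss is also partial. A suppressed ACTH result still counts in the Overall row and appears in the listing. The chemistry and urine shift shells have a highest post-baseline row, which would show a range category if they cover these parameters, but not the Week 4 change from baseline.

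Two stronger inferences are tempting but unsupported:
- A reader might infer that SAP 7.2 contradicts section 7, because its major-deviation list includes "Week 4 assessments performed more than 14 days after the scheduled date". That list grades deviations, is not exhaustive and is finalised at the data review meeting. It does not define analysis visits.
- A reader might infer that the ACTH listing proves such moves are intended, because its footnote "indicates reported visit is different from the analysis visit after windowing was performed" allows relabelling. The same footnote stands under many listings and fits an unscheduled test assigned to Week 4 or Week 8 equally well.

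**Conclusion.** The point holds as a defect in the wording of the rule. On its literal text, Week 4 tests on days 36–40 and days 18–21, and Week 8 tests on days 46–49, are assigned to visits that the primary tables do not show. A competing Week 6 repeat can push a late Week 4 calcium or urine result into the listings alone. The narrower reading removes most of the ACTH problem but leaves calcium and urine open.

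A reader might go further and conclude that primary results have been lost or that the Week 4 suppression rate is understated. The documents do not support that. Visits are planned within ± 2 days, a test must be at least 7 days late (or 8 early) before anything moves, and nothing shows that any was. The 1/7 versus 0/6 contrast also requires that the one displaced subject be the only event.

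The analysis is descriptive, and the protocol says of its size: "The choice of sample size in this trial is not based on statistical considerations". The consequence would therefore be a missing subject and a wider interval in a small table, not an altered test. With 7 subjects and one affected, the upper limit for zero events moves from 41.0% to 45.9%. The correction is cheap and should be made.

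**What to change.** Add to SAP section 7, for ACTH, serum calcium and morning urine:
- Post-baseline out-of-window results may be assigned only to Week 4 or Week 8, never to a pre-treatment visit.
- A test recorded as Week 4 or Week 8 keeps that visit if it was done within 14 days of the target day (days 15–43 for Week 4, days 43–71 for Week 8). The recorded visit then settles the day 43 tie, which restricting the eligible visits alone would not do.
- Conditional Week 6 repeats stay labelled as repeats and do not displace the Week 4 result.

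The sponsor should also say whether the 14-day limit applies to unscheduled and early-termination results, which carry no Week 4 or Week 8 label.

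The cost is a few sentences and a per-assessment window lookup in programming. SAP section 2 allows revision before the interim database lock and foresees a separate SAP for any final analysis. No listing change is needed, because the ACTH, serum biochemistry and morning urine listings already show the study day. The downside is that the Week 4 and Week 8 rows may include tests up to 14 days off target; these can be flagged in a footnote.

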7.1. Subject Disposition

The following disposition summaries will be provided:

- A summary of the number of subjects who provided the informed consent / informed assent, the number of screen failures (including those subjects who satisfied the inclusion/exclusion criteria but for whom no study drug was dispensed) with reasons for premature study termination
- A summary of the number of screen failure subjects violated any inclusion/exclusion criterion,

**MC2-01-C6_STATISTICAL ANALYSIS PLAN_Final 3.0_07 September 2020**

by criterion

- A summary of the number of subjects allocated to treatment, the number and percentage of subjects attended each study visit (Allocated to treatment set)
- A summary of the number and percentage of subjects included in each population for statistical analysis (Allocated to treatment set)
- A summary of the number and percentage of subjects completed the study and prematurely discontinued from the study by reason for study discontinuation (Allocated to treatment set)
- A summary of the number and percentage of subjects completed the study treatment and prematurely discontinued the study treatment before Week 8 visit by reason for discontinuation (Safety population).

By-patient listings of disposition details will be provided for all enrolled subjects.

7.2. Protocol Deviations

Number and percentage of subjects with at least one protocol deviation and at least one major protocol deviation will be tabulated by category and subcategory and overall (Allocated to treatment set). All protocol deviations will be listed (All Enrolled subjects).

Major protocol violations include but are not limited to:

- Informed consent not received or provided after the first study visit;
- Inclusion/exclusion criteria violations in subjects allocated to treatment;
- Use of prohibited concomitant medication or non-drug therapy that may affect study results or their interpretation;
- Week 4 assessments performed more than 14 days after the scheduled date;
- Week 8 assessments performed more than 14 days after the scheduled date;

Major protocol violations will be finalized and approved by MC2 at the data review meeting.

7.3. Demographic and Baseline Variables

eCRF form: “DEMOGRAPHICS”, “VITAL SIGNS”.

Descriptive statistics for the following demographic, anthropometric and other baseline characteristics will be presented in accordance with section 7:

- demographic characteristics: country, age, gender, race, ethnic origin;
- anthropometric characteristics: height (cm), weight (kg), body mass index (BMI, kg/m²);

**MC2-01-C6_STATISTICAL ANALYSIS PLAN_Final 3.0_07 September 2020**

eCRF form: “FITZPATRICK SKIN TYPE ASSESSMENT”, “BODY SURFACE AREA INVOLVEMENT ASSESSMENT”, “PHYSICIAN’S GLOBAL ASSESSMENT OF PSORIASIS SEVERITY”, “MAIN DIAGNOSIS”, “LOCAL SKIN REACTIONS ASSESSMENT”.

- Fitzpatrick skin type;
- Scalp BSA psoriatic involvement (%), Neck, Trunk and/or Limbs BSA psoriatic involvement (%), Total psoriatic involvement (%);
- Physician’s Global Assessment of psoriasis severity (PGA);
- Duration of disease (months);

Specific calculations and/or conversions include but are not limited to the following:

Body mass index will be calculated as $weight \text{ (kg)} / [height \text{ (m)}]^2$.

Duration of disease will be calculated in months as $(date \text{ of informed consent} - date \text{ of diagnosis} + 1) / 30.4375$. In order to calculate disease duration partial diagnosis date will be imputed with 15th day of the same month, if month and year of diagnosis are collected. If only year of diagnosis is collected, diagnosis date will be imputed as July 1st of the corresponding year. If the imputed date of diagnosis is later than the date of informed consent, the date of informed consent will be used.

All data will be listed.

7.4. Concurrent Illnesses and Medical Conditions⁵

eCRF form: “MEDICAL HISTORY”

Medical history findings will be coded using the Medical Dictionary for Regulatory Activities (MedDRA) version 22.0 (or more recent version if available) according to Data MATRIX SOP [4], and will be presented by Primary System Organ Class (SOC) and Preferred Term (PT) within SOC.

Prior and concurrent diagnoses will be tabulated separately.

Medical history findings will be reported on a by-patient basis. This implies that if the subject suffered the same event (mapped to same PT) repeatedly the event will be counted once and only once for appropriate PT. Within SOC subjects may have reported more than one PT. The SOCs and PTs within each SOC will be sorted in descending order of total incidence.

Classification of condition/diagnosis as either Prior or Concurrent will be based on stop date of condition/diagnosis in “MEDICAL HISTORY” eCRF form. The number (%) of subjects reporting any medical history will be presented in tables by SOC and PT.

Medical history records with stop date prior to the date of first dose of study therapy will be classified as Prior conditions/diagnoses. If a condition/diagnosis stops on or after the date of first

⁵ This section is based on the section 7.1 “Demographics and Medical History” of clinical study Protocol.

